# 13.5. Importance of nurse-sensitive factors

Nutritional therapy appears to be a complex intervention that acts on different levels. While EFFORT focuses primarily on the efficacy of the nutritional strategy, other elements, such as nurse-sensitive factors, may be of particular importance in the successful implementation of such a strategy in "real life." To further shed light on this important topic, we will in collaboration with Prof. [name] of the Institute of Nursing Science, University of Basel, develop a protocol to study the importance of various nurse-sensitive factors (e.g., nurse workload, nurse staffing, nursing staff attitudes towards nutritional therapy) on our intervention. For this purpose, we will at all study sites collect caregiver-level data and conduct interviews with nursing staff. We will then investigate whether such factors help account for differences

in the magnitude of patient response to our intervention. Specifically, we will test for effect modification within our regression model using a hierarchical approach. A more detailed proposal will be developed in the later preparation phase of the trial.

# 14. Schedule and milestones

EFFORT includes several research aims which will consecutively be accomplished as demonstrated below. For the prospective trial, we will do a 3-6 month pilot-phase with step-wise inclusion of study centers followed by a 2-year (maximal 3 year) active patient recruitment period. Thereafter, we have dedicated 18 month to complete the 6 month long term follow-up of all patients, and finish all primary and secondary aims and ancillary projects.

	Jan -	-	Jul -	Jan -						
Objectives	Jun		Dec	Jun	Dec	Jun	Dec	Jun	Dec	Jun
	2014	1	2014	2015	2015	2016	2016	2017	2017	2018
Main trial										
Finalization of protocol, ethical approval										
Pilot phase, stepwise inclusion of centers										
Active patients enrollment in all centers										
Database finalization and 6-month follow-up										
Data analysis and manuscript preparation										
Manuscript publication										
Physio-pathological effects										
Data analysis										
Manuscript preparation and publication										
Cost-effectiveness analysis										
Data analysis										
Manuscript preparation and publication										

#### 15. Potential limitations

We are aware of several potential limitations to the successful completion of this trial. First, inclusion of 3000 patients over a 2-year time frame is ambitious. However, based on our experience from previous multicenter randomized trials, our well-established multicenter research network, the conceptual and logistical support from the University of Basel CTU, and the large total population of patients potentially eligible for this trial who are hospitalized at the study centers, we are convinced that the trial is feasible. Pilot data from a current observational cohort study have shown that the University Department of Medicine at the Kantonsspital Aarau by itself has about 8,000 medical hospitalizations per year, among which about 1,500 − 2,000 patients have an NRS≥3 points and a LOS≥5 days and would thus be enrollment candidates. Also, before active recruitment begins, we have planned a pilot feasibility period to validate all trial-related material as well as the intervention. Last-minute protocol enhancements to address "real-world issues" (if any) would be possible.

As a second limitation, there is no blinding of patients or caregivers regarding the randomization arm, which might introduce bias. However, outcome assessment at day 30, including for the primary endpoint and most secondary endpoints will be blinded. Due to the variety of nutritional options to reach the nutritional goals, we felt that a placebo control group would be neither feasible, nor ethical.

Third, there is potential for control group "contamination", i.e., if the caregiver staff feels obliged to motivate patients in the control group to increase their food consumption. A complex intervention such as nutritional therapy must be implemented at different levels and by the full care team in the hospital. While dieticians recommend individualized strategies for patients, the physician staff need to support the strategy and motivate the patient, and, most importantly, the nursing team is key in everyday application of the strategy, i.e., actively encouraging, and if needed, feeding the patient. It will thus be important to continuously educate the caregiver staff about the intention of this trial, and the potential risks of nutritional therapy which have not yet been well-studied in the population in question. We will also study caregiver characteristics (e.g., nurse—sensitive factors potentially affecting outcome, such as nursing staff work load) to detect any impact of these variables on our intervention (ancillary project).

Fourth, it is expected that not all patients in the intervention group reach their caloric and protein goals and some may refuse enteral and parenteral nutrition. However, as a pragmatic, trial we are most interested in the effects of nutritional therapy in "real life" using a state-of-the-art algorithm. Still, we will document actual nutritional intake and later study the effect of compliance on our intervention.

# 16. Importance and impact of the proposed project

Nutrition is essential for survival and function in health and disease. Despite its centrality to hospital practice, nutritional therapy has not been well-studied and high-quality evidence of efficacy, safety and cost-effectiveness in acutely-ill medical inpatients outside critical care is lacking. These gaps and ambiguities in the literature and recent evidence from critically ill patients suggesting potential harmful effects of nutritional therapy are of concern.

By integrating international expertise, a strong research infrastructure, comprehensive meta-analysis, and an original, large-scale, interventional RCT, EFFORT aims to establish an evidence-based standard for nutritional therapy in medical inpatients. Additionally, using a physio-pathological mechanistic approach, EFFORT will increase basic understanding on how nutrition affects acute disease and vice versa. Further, by incorporating pharmaco-economic research, EFFORT will elucidate the indications in which nutritional therapy, which because of its widespread application currently is associated with substantial costs, is cost-effective and those in which it is not. By generating these data, EFFORT will facilitate more efficient healthcare resource distribution.

In the centerpiece of EFFORT, we shall test this strategy in the largest-yet nutritional RCT outside critical care to provide definitive evidence about expected benefits and harms of this intervention. Additionally,

we shall capitalize on the EFFORT RCT to study physio-pathological mechanisms associated with the interplay of nutrition and disease, and to measure the value of nutritional therapy.

This pragmatic comparative effectiveness research project thereby will improve the quality, effectiveness, safety and efficiency of nutritional therapy and basic understanding of the relationship between nutrition and illness. Data acquired through EFFORT will help healthcare professionals and payers worldwide to make better-informed decisions regarding care of frail, elderly and polymorbid individuals with acute illness, who represent a large and growing patient population worldwide, and one that accounts for a major share of medical resource consumption. We thus expect that the results of all aims of the EFFORT project will be widely, directly and rapidly applied – and indeed, will contribute to a new standard of care – in hospital clinical practice worldwide.

# **APPENDIX**

# **APPENIDX 1. Barthel index (German version)**

Aktivitäten des täglic	hen Lebens (ADL), Barthel-Index	Patientendalen
Datum:		

1. Essen	Punkte
Unabhängig, benutzt Geschirr und Besteck	10
Braucht Hilfe, z.B. beim Schneiden	5
Total hilfsbedürftig	0
2. Baden	,
Badet oder duscht ohne Hilfe	5
Badet oder duscht mit Hilfe	0
3. Waschen	,
Wäscht Gesicht, kämmt, rasiert bzw. schminkt sich, putzt Zähne	5
Braucht Hilfe	0
4. An- und Auskleiden	, i
Unabhängig, inkl. Schuhe anziehen	10
Hilfsbedürftig, kleidet sich teilweise selbst an/aus	5
Total hilfsbedürftig	0
5. Stuhlkontrolle	
Kontinent	10
Teilweise inkontinent	5
Inkontinent	0
6. Urinkontrolle	
Kontinent	10
Teilweise inkontinent	5
Inkontinent	0
7. Toilettenbenutzung	
Unabhängig bei Benutzung der Toilette/des Nachtstuhls	10
Braucht Hilfe für z.B. Gleichgewicht, Kleidung aus-/anziehen, Toilettenpapier	5
Kann nicht auf Toilette/Nachtstuhl	0
8. Bett-/(Roll-)Stuhltransfer	,
Unabhängig (gilt auch für Rollstuhlfahrer)	15
Minimale Assistenz oder Supervision	10
Kann sitzen, braucht für den Transfer jedoch Hilfe	5
Bettlägerig	0
9. Bewegung	
Unabhängiges Gehen (auch mit Gehhilfe) für mindestens 50 m	15
Mindestens 50 m Gehen, jedoch mit Unterstützung	10
Für Rollstuhlfahrer: unabhängig für mindestens 50 m	5
Kann sich nicht mindestens 50 m fortbewegen	0
10. Treppensteigen	
Unabhängig (auch mit Gehhilfe)	10
Braucht Hilfe oder Supervision	5
Kann nicht Treppensteigen	0
Gesamtpunktzahl (max. 100)	'

# APPENIDX 2. Nutritional risk screening (NRS, 2002)

# Screening auf Mangelernährung im Krankenhaus Nutritional Risk Screening (NRS 2002)

nach Kondrup J et al., Clinical Nutrition 2003; 22: 415-421

Empfohlen von der Europäischen Gesellschaft für Klinische Ernährung und Stoffwechsel (ESPEN)

# Vorscreening:

Ist der Body Mass Index < 20,5 kg/m²?

- lja Inein
- · Hat der Patient in den vergangenen 3 Monaten an Gewicht verloren?
- 1 ja 1 nein
- · War die Nahrungszufuhr in der vergangenen Woche vermindert?
- 1 ja 1 nein

· Ist der Patient schwer erkrankt? (z.B. Intensivtherapie)

- 1 ja 1 nein
- ⇒ Wird eine dieser Fragen mit "Ja" beantwortet, wird mit dem Hauptscreening fortgefahren
- ⇒ Werden alle Fragen mit "Nein" beantwortet, wird der Patient wöchentlich neu gescreent.
- ⇒ Wenn für den Patienten z.B. eine große Operation geplant ist, sollte ein präventiver Ernährungsplan verfolgt werden, um dem assoziierte Risiko vorzubeugen.

#### Hauptscreening:

Störung des Ernährungszustand:	s Punkte
Keine	0
Mild	1
Gewichtsverlust > 5%/ 3 Mo. oder N zufuhr < 50-75% des Bedarfes in de vergangenen Woche	
Mäßig	2
Gewichtsverlust > 5%/ 2 Mo. oder B 20,5 kg/m  und reduzierter Allgemeinzustand (/ oder Nahrungszufuhr 25-50% des B in der vergangenen Woche	AZ)
Schwer  Gewichtsverlust> 5% /1 Mo. (>15% oder BMI <18,5 kg/m² und reduziert meinzustand oder Nahrungszufuhr (des Bedarfes in der vergangenen W	er Allge- 0-25%

Krankheitsschwere	Punkte
Keine	0
Mild	1
z.B. Schenkelhalsfraktur, chronisch kungen besonders mit Komplikatio Leberzirrhose, chronisch obstruktiv Lungenerkrankung, chronische Hä Diabetes, Krebsleiden	nen: ⁄e
Mäßig	2
z.B. große Bauchchirurgie, Schlags schwere Pneumonie, hämatologisc Krebserkrankung	-
Schwer	3
z.B. Koofverletzung, Knochenmark	trans-

plantation, intensivpflichtige Patienten

(APACHE-II >10)

1 Punkt, wenn Alter ≥ 70 Jahre

≥ 3 Punkte	Ernährungsrisiko liegt vor, Erstellung eines Ernährungsplanes
< 3 Punkte	wöchentlich wiederholtes Screening. Wenn für den Patienten z.B. eine große
	Operation geplant ist, sollte ein präventiver Ernährungsplan verfolgt werden, um das assoziierte Risiko zu vermeiden.

T. Schütz, L. Valentini, M. Plauth. Screening auf Mangelemährung nach den ESPEN-Leitlinien 2002. Aktuel Ernacht Med 2005; 30: 99-103.

# **APPENIDX 3. Quality of life (EQ 5D)**

Bitte geben Sie an, welche Aussagen Ihren heutigen Gesundheitszustand am besten beschreiben, indem Sie ein Kreuz in ein Kästchen jeder Gruppe machen.

Beweglichkeit/Mobilität	
Ich habe keine Probleme herumzugehen	
Ich habe einige Probleme herumzugehen	
Ich bin ans Bett gebunden	
Für sich selbst sorgen	
Ich habe keine Probleme, für mich selbst zu sorgen	
lch habe einige Probleme, mich selbst zu waschen oder mich anzuziehen 🚨	
Ich bin nicht in der Lage, mich selbst zu waschen oder anzuziehen	
Allgemeine Tätigkeiten (z.B. Arbeit, Studium, Hausarbeit, Familien- oder Freizeitaktivitäten)	
Ich habe keine Probleme, meinen alltäglichen Tätigkeiten nachzugehen	
Ich habe einige Probleme, meinen alltäglichen Tätigkeiten nachzugehen	
lch bin nicht in der Lage, meinen alltäglichen Tätigkeiten nachzugehen	
Schmerzen/körperliche Beschwerden	
Ich habe keine Schmerzen oder Beschwerden	
Ich habe mässige Schmerzen oder Beschwerden	
Ich habe extreme Schmerzen oder Beschwerden	
Angst/Niedergeschlagenheit	
Ich bin nicht ängstlich oder deprimiert	
Ich bin mässig ängstlich oder deprimiert	
Ich bin extrem ängstlich oder deprimiert	

denkbarer

100

Um Sie bei der Einschätzung, wie gut oder wie schlecht Ihr Gesundheitszustand ist, zu unterstützen, haben wir eine Skala gezeichnet, ähnlich einem Thermometer. Der best denkbare Gesundheitszustand ist mit 100 gekennzeichnet, der schlechteste mit 0.

Wir möchten Sie nun bitten, auf dieser Skala zu kennzeichnen, wie get oder schlecht Ihrer Ansicht nach Ihr persönlicher Gesundheitszustand heute ist. Bitte verbinden Sie dazu den unten stehenden Kasten mit dem Punkt auf der Skala, der Ihren heutigen Gesundheitszustand am besten wiedergibt.

Ihr

heutiger Gesundheitszustand 6**±**0

Schlechtest denkbarer Gesundheitszusta

# **APPENIDX 4. Nutritional guidelines (German version)**

Nutrition Risk Screening (NRS) innerhalb 24-48Std. nach Spitaleintritt

wenn NRS ≥ 3 Punkte → individuelles Assessment des Patienten
Malnutrition vorhanden? Ernährungstherapie gewünscht und sinnvoll?
wenn Ja → Festlegung einer Strategie zur Erreichung von individuellen Ernährungszielen

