# Synopsis

Sponsor / Sponsor- Investigator	[name]. med. [name]., MPH; Department of Endocrinology, Diabetes and Clinical Nutrition; University Department of Internal Medicine, Kantonsspital Aarau, [name]	
Study Title:	Full Title: Effect of Early Nutritional Therapy on Frailty, Functional Outcomes and Recovery of Undernourished Medical Inpatients Trial: The EFFORT Project	
Short Title	The EFFORT trial	
Protocol Version	EKNZ 2014_001 (version 3.3, 27.3.2014)	
Trial registration:	This trial will be registered at www.ClinicalTrials.gov	
Study category and Rationale	Category A (nutritional products used are authorised in Switzerland and the application is done according to the specialised information	
Clinical Phase:	Confirmation study regarding effectiveness and safety of nutritional therapy in medical inpatients	
Background and Rationale:	Illness is associated with appetite loss leading to relevant nutritional deficits, particularly in elderly, frail medical inpatients. Undernutrition is associated with morbidity, long hospital stays and costs. Despite these associations, benefit of providing early nutritional therapy to unselected medical inpatients at risk for undernutrition remains largely unproven due to lack of large-scale, high-quality randomized controlled trials (RCTs). Therefore, a large conclusive trial is urgently needed to answer the questions (a) whether or not appetite loss during acute illness is indeed a protective physiological response that should be tolerated; (b) which patients do or do not benefit from nutritional therapy; (c) how and why nutrition affects the course of disease from a mechanistic physio-pathological standpoint.	
Objective(s):	To test the hypothesis that in medical inpatients at risk for undernutrition defined by the nutritional risk score (NRS 2002), early tailored nutritional therapy to reach nutritional targets based on individualized nutritional counseling is a cost-effective strategy to prevent mortality, morbidity and functional decline.	

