Outcome(s):	The primary composite endpoint is combined adverse outcome within 30 days defined as (a) all-cause mortality, (b) admission to the intensive care unit from the medical ward, (c) major complications, (d) unplanned hospital readmissions and (d) decline in functional outcome from admission to day 30 assessed by Barthel's index (-10%). Secondary endpoints include (a) each single component of the primary endpoint (b) short-term nutritional and functional outcomes from inclusion to day 10 or hospital discharge; (c) hospital outcomes; (d) 30-day and 180-day outcomes (e) Other safety endpoints including adverse gastrointestinal effects associated with nutritional therapy assessed daily until hospital discharge.	
Study design:	Randomized controlled trial	
Inclusion / Exclusion criteria:	Unselected adult medical inpatients at risk of undernutrition [NRS≥3 points] and an expected hospital stay of ≥5 days who are willing to provide informed consent will be included. We will exclude patients in critical care or post-operative state, unable to swallow, at long-term need for parenteral/enteral nutrition, in terminal condition, pregnant, with acute pancreatitis or acute liver failure, with anorexia nervosa, that were earlier included into the trial	

Measurements and procedures:	Patients in the intervention group will receive individualized nutritional therapy to reach nutritional targets (caloric, protein, micronutrients, other) based on a predefined nutritional strategy. In control patients, according to patients' appetite, standard hospital nutrition will be served. Nutritional therapy may be started in control patients, if any sort of swallowing disorders develops or if patients need to be prepared for operation. All patients will be re-assessed daily during the hospital stay for nutritional intake and nutritional therapy may be escalated every 24-48 hours (food fortification, oral supplements, enteral, parenteral nutrition) if targets are not met (at least 75% of targets).		
Study Product / Intervention:	Different nutritional products (oral nutritional supplements, enteral nutrition, parenteral nutrition) to reach nutritional targets		
Control Intervention:	Usual care;		
Number of Participants with Rationale:	The inclusion of 2000-3000 patients will provide 78-90% power to detect a reduction in the primary endpoint of 15% (from 40% to 34%)		

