# 3.2. Objective

Our aim is to conduct a large investigator-initiated, non-commercial RCT to compare a "state-of-the-art" individualized nutritional therapy strategy to cover nutritional requirements based on pre-specified nutritional therapy guidelines (intervention group) versus a control group without nutritional therapy in a large representative medical inpatient population at risk for malnutrition.

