#### 5.2. Inclusion criteria

Included will be all consecutive medical inpatients if they meet the following criteria

- a) NRS ≥3 points
- b) expected hospital LOS ≥5 days (as estimated by the treating physician team)
- c) willingness to provide informed consent (see informed consent statement)

[figure not shown]

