#### 6.1. Intervention

For the purpose of this study, we have developed nutritional guidelines by consensus and adapted to current guidelines (e.g., ESPEN, ASPEN)  (*figure 1 and Appendix 4*). Guidelines specify a reinforced nutritional therapy strategy to cover nutritional requirements, focusing on nutritional targets based on the specific nutritional diagnoses defined by the IDNT. The nutritional guidelines may vary according to important medical diagnoses (i.e. renal failure). They specify not only nutritional targets, but also escalation of the route (i.e. food fortification, oral, enteral, parenteral) if targets cannot be achieved (≤75%) every 24-48 hours.

Nutritional goals will be assessed daily in patients in the intervention group (*Figure 2*). In control patients, we will use conventional nutrition according to the ability and desire of the patient to eat, using standard care food provided by the hospital kitchen ("appetite-guided").

Nutritional therapy may be started in control patients at any time, if new swallowing disorders develop or if patients need to be prepared for surgical interventions. Similarly, nutritional therapy may be stopped in case patients in the intervention group become terminal or develop a condition where nutritional therapy is contraindicated (e.g., intestinal perforation). Thus, in both groups the nutritional therapy protocol may be overruled after discussion with the PI and the involved study coordinators.

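### Appendix 4 makes the nutritional strategy conditional on malnutrition being present, whereas the rest of the protocol gives it to every intervention patient at risk (NRS ≥3)

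*Protocol*

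**What the plan says.** Section 6.1 says that nutritional guidelines were developed for this study and refers for them to "figure 1 and Appendix 4". Section 4.3 escalates intervention patients who miss their targets according to those guidelines. Appendix 4 is therefore operative text.

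Its opening lines run as follows. Screening takes place within 24-48 hours of admission, and NRS ≥3 leads to an individual assessment. Two questions follow: "Malnutrition vorhanden? Ernährungstherapie gewünscht und sinnvoll" (is malnutrition present; is nutritional therapy wanted and sensible). Then comes "wenn Ja → Festlegung einer Strategie zur Erreichung von individuellen Ernährungszielen": if yes, a strategy is set to reach individual nutritional goals. No branch is given for a no.

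Elsewhere the condition is risk alone. Section 3.2 sets the comparison "in a large representative medical inpatient population at risk for malnutrition". Section 5.2 asks for NRS ≥3, an expected stay of at least 5 days and consent. Section 5.3 does not exclude patients who are not malnourished, and section 4.3 randomises on those criteria and consent. The synopsis states: "Patients in the intervention group will receive individualized nutritional therapy to reach nutritional targets". At 3 points or more, the form in Appendix 2 declares nutritional risk present and calls for a nutrition plan, with no further question.

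**The concern.** The chart that sites are to follow contains a condition for starting the tested strategy that the objective, the eligibility criteria, the randomisation section and the synopsis do not contain. At issue is which intervention patients get the intervention. If a dietician answers the malnutrition question literally, an eligible patient at risk could be randomised to nutritional therapy and receive no strategy. Section 8.1 keeps all randomised patients in the primary analysis, so that patient would still count in the intervention arm. Sites reading the same line differently would deliver different interventions under one protocol.

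**Working it through.** The plan gives no figure on this point, so the check has two parts: whether the malnutrition question merely repeats NRS ≥3, and what each section prescribes for a patient in whom the two differ.

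**Can a patient be eligible with no scored nutritional impairment?** The inputs come from Appendix 2: nutritional status N (0 to 3), severity of disease S (0 to 3), and age A (1 point if 70 or over, otherwise 0). The total is NRS = N + S + A.

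With N = 0 there are 4 × 2 = 8 combinations of (S, A):

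- (0,0) = 0; (0,1) = 1
- (1,0) = 1; (1,1) = 2
- (2,0) = 2; (2,1) = 3
- (3,0) = 3; (3,1) = 4

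Three of the 8 reach NRS ≥3. This counts score combinations, not patients. Two of the three need S = 3, and the examples given for that grade are mostly excluded by section 5.3 (critical care under a, stem cell transplantation under m). That leaves mainly 0 + 2 + 1 = 3, for example severe pneumonia at age 70 or over.

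This patient can also pass the pre-screening, which needs one yes. Any weight loss in the past 3 months is enough, while a loss of 5% or less scores 0 in the main screening. NRS ≥3 is therefore not the same as malnutrition being present.

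**What each section prescribes for this patient**, assuming an expected stay of at least 5 days, consent and no exclusion:

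- Sections 5.2, 5.3 and 4.3: eligible, and randomised.
- Appendix 2: a nutrition plan is drawn up.
- Synopsis, if allocated to the intervention: individualised therapy to reach targets.
- Appendix 4: a strategy if malnutrition is judged present; nothing is stated otherwise.
- Section 8.1: included in the primary analysis whatever was delivered.

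**When is the question asked?** Appendix 4 does not say. Section 4.4 places the dietician's structured medical and nutritional assessment after trial inclusion. If that is the individual assessment in the chart, the question falls to patients already included.

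**Does an existing provision cover a no?** Section 6.1 gives terminal illness and a new contraindication as reasons to stop therapy. Section 15 foresees missed targets and refusal of enteral or parenteral nutrition. Neither describes a patient judged not malnourished. The general clause in 6.1, "Thus, in both groups the nutritional therapy protocol may be overruled after discussion with the PI and the involved study coordinators", could be stretched to such a patient, but it requires a discussion that the chart's question does not.

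**The case against.** The strongest reply is that the phrase is loose wording for being at risk. The protocol is not strict with these terms: its full title speaks of undernourished patients, and the Appendix 2 form is headed as a screening for malnutrition yet ends in a plan at 3 points. The chart also gives no instruction to withhold therapy. Its later decision points carry both a yes and a no branch, while this one has only a yes, and one could argue that the yes belongs to the second question alone. All of this is plausible and keeps the point small. It does not remove the conflict, because the words as printed put the malnutrition question before the strategy. If they only restate risk, or have no yes attached, they do no work and can be deleted without loss.

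Second, the protocol has a diagnostic standard. Sections 4.4 and 6.1 refer to IDNT nutritional diagnoses, and 6.1 bases targets on them. A reader might infer that malnutrition is left wholly without a definition; that goes too far. What stands is that neither section links IDNT to this question, and that a definition would not settle the conflict with an at-risk population.

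Third, the question whether therapy is sensible is also a bedside judgement under the same yes. That is fair. Consent (5.2c), exclusions 5.3g and 5.3n and the 6.1 route largely cover it, and the sentence proposed for 6.1 would send any remaining case through that route.

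**Conclusion.** The contradiction about who receives the strategy holds and is minor. Appendix 4 read literally and the rest of the protocol give different answers for an eligible intervention patient judged not malnourished, and at least one ordinary clinical profile (0 + 2 + 1 = 3) can produce such a patient. That this could leave a randomised patient untreated rests on two assumptions: that staff apply the line as printed, and that the chart's assessment is the one section 4.4 places after inclusion.

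Three stronger readings are tempting, and the documents do not support them.

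- **Loss of power.** Untreated patients in the intervention arm would dilute the effect, but the protocol gives no share of patients who would be judged not malnourished. The number affected is unknown, and the stated sample size is not called into question.
- **A distorted NRS subgroup test (3, 4, >4).** Patients with 0 nutritional-status points cannot exceed NRS 4, so a reader might expect the strategy to be withheld only at low NRS. That requires not malnourished to mean 0 status points, which Appendix 4 does not say.
- **A hidden eligibility criterion.** This would need the question to be asked before randomisation. Section 4.3 randomises on the listed criteria and consent, and section 4.4 points to a later assessment.

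**What to change.** Delete the two words *Malnutrition vorhanden* with their question mark from the trial version of Appendix 4. Add one sentence to section 6.1: every patient randomised to the intervention group receives nutritional targets and a strategy, with departures only after discussion with the PI and the study coordinators, as 6.1 already provides, and each departure is recorded.

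The cost is two words removed and one sentence added. Sample size, schedule and analysis do not change, and nothing is lost if the phrase was only loose wording.
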